8.2 Study termination

This study may be suspended or terminated if there is sufficient reasonable cause. The Sponsor/Investigator will notify the co-investigators and Verastem if he/she decides to discontinue the study. If the study is prematurely closed, the clinical investigators will notify the study participants, and the Sponsor/Investigator will notify the IRB/IEC, and the FDA. Reasons for suspension and termination of the study include:

- Determination of unexpected or unacceptable risk to patients
- Demonstration of efficacy that would warrant stopping
- Determination of futility
- Insufficient compliance to protocol requirements
- Determination that the primary endpoint has been met

The study may resume once concerns about safety and compliance have been addressed and are satisfactory with sponsor and IRB/IEC.

9. Inclusion and Exclusion Criteria

9.1 Inclusion Criteria

1. Hospitalized in participating facility.
2. Documentation of pneumonia with radiographic evidence of infiltrates by imaging (e.g., chest x-ray or CT scan).
3. Laboratory-confirmed SARS-CoV-2 infection as determined by PCR or other authorized or approved assay in any specimen collected within 72 hours prior to enrollment. Note – An exception must be requested to the Sponsor if ≥72 hours since positive test.
4. Symptoms suggestive of severe systemic illness with COVID-19, such as respiratory rate ≥ 30 breaths per minute, heart rate >125 beats per minute, oxygen saturation (O₂ sat) in the blood of <93% on room air at sea level or PaO₂/FiO₂ < 300 (see Appendix A).
5. 18 years of age or older
6. Patients with hematological parameters at screening consistent with ≤ grade 2 NCI CTCAE v5.0 toxicity: hemoglobin ≥8 g/dL, platelet count ≥50,000 K/mcl, an absolute neutrophil count (ANC) ≥1,000/mm³, and an absolute lymphocyte count (ALC) ≥500/mm³.

Protocol Title: Duvelisib Ameliorates Manifestations of Pneumonia in Established Novel Coronavirus Infection (DAMPEN-CI)

7. Patients with laboratory measurements of liver function at screening consistent with \leq grade 2 NCI CTCAE v5.0 toxicity: alanine aminotransferase (ALT) \leq 5X ULN; aspartate aminotransferase (AST) \leq 5X ULN; and bilirubin \leq 3X ULN.
8. The effects of duvelisib on the developing human fetus are unknown. For this reason, women of child-bearing potential (WOCBP) must have a negative serum or urine pregnancy test prior to starting therapy. WOCBP and men must agree to use adequate contraception (hormonal or barrier method of birth control; abstinence) from enrollment into this study until at least 60 days after the first dose of duvelisib. A woman of childbearing potential (WOCBP) is a sexually mature woman who: 1) has not undergone a hysterectomy or bilateral oophorectomy; or 2) has not been naturally postmenopausal for at least 24 consecutive months (i.e., has had menses at any time in the preceding 24 consecutive months. Should a woman become pregnant or suspect she is pregnant while she or her partner is participating in this study, she should inform her treating physician immediately. Men treated or enrolled on this protocol must also agree to use adequate contraception prior to the study, for the duration of study participation, and 2 months after completion of duvelisib administration. WOCBP must have a negative pregnancy test after admission to the hospital, prior to the first dose of study drug.

The patient must be willing to comply with fertility requirements as below:

- Total abstinence (when this is in line with the usual practice and lifestyle of the patient) will be accepted. Periodic abstinence (i.e., calendar, ovulation, post-ovulation methods) and withdrawals are not acceptable forms of contraception. All other patients must comply with the measures described below.
- If a female participant is of reproductive potential, the participant (and her partner) must agree to use of one of the following combinations of birth control during the study and for 2 months after the last dose of study drug (or tubal ligation as a single method):
 - 1) Use of a double-barrier method of contraception: condoms (male or female) and a diaphragm or cervical cap with spermicide;
 - 2) Use of an IUD and a barrier method: condoms (male or female, with or without spermicide) or a diaphragm or cervical cap with spermicide;
 - 3) Tubal ligation.
- Women who are post-menopausal, defined as age greater than 45 and no menses for at least 24 consecutive months, or who have had a hysterectomy, are considered not of reproductive potential.
- Males must agree to using contraception during the study and for 2 months after the last dose of study drug or have undergone a male sterilization procedure (at least 6 months prior to screening).
- Use of oral (estrogen and progesterone), injected or implanted hormonal methods of contraception, or placement of an intrauterine device (IUD) or intrauterine system (IUS) or other forms of contraception that comparable efficacy (failure rate $<1\%$). In case of oral contraception, the woman should be stable on the same pill for a minimum of 3 months prior to enrollment on the study.
- 5. Patients must agree not to donate blood, sperm/ova or any other organs while taking protocol therapy and for at least 2 weeks after stopping treatment.
- 6. Willingness and ability of the patient to comply with scheduled visits, drug administration plan, protocol specified laboratory tests, other study procedures and study restrictions
- 7. Evidence of personally signed informed consent indicating that the subject is aware of the life-threatening nature of the disease and has been informed on the procedures to be followed, the experimental nature of the therapy, alternative, potential risks and discomforts, potential benefits and other pertinent aspects of study participation.

9.2 Exclusion criteria

Protocol Title: Duvelisib Ameliorates Manifestations of Pneumonia in Established Novel Coronavirus Infection (DAMPEN-CI)

1. Patients requiring mechanical ventilation (e.g. intubation, high-flow O₂ Bi-PAP or AIRVO) at the time randomization.
2. Patients receiving any investigational drugs other than drugs or therapies to treat COVID-19, with the exception of investigational immune-modulatory drugs as per section 5.4.
3. Pregnant women are excluded from this study because duvelisib is agent with the potential for teratogenic or abortifacient effects. Because there is an unknown but potential risk for adverse events in nursing infants secondary to treatment of the mother with duvelisib, breastfeeding should be discontinued before starting study drug and breastfeeding should not be resumed until at least 1 month after last dose of study drug.
4. Clinical suspicion that the etiology of acute illness (acute decompensation) is primarily due to a condition other than COVID-19
5. Known contraindication to duvelisib
6. Patients with hepatic cirrhosis as defined by symptomatic liver dysfunction; liver fibrosis by biopsy; ALT > 5X ULN, AST > 5X ULN, or bilirubin > 3XULN.
7. Patients with autoimmune diseases or patients on chronic immunosuppressive medications at the time of hospital admission or screening.
8. Active Hepatitis B or C infection, as determined by FDA-approved serology testing.

10. Number of Participants

We will be recruiting a total of 80 participants at Emory Healthcare and potential secondary sites, combined. We are expecting to have to consent 100 number of participants to reach our recruitment goal of 80. Patients will be registered after signing of the informed consent document and meeting all entry requirements.

11. Recruitment Methods

Investigators, nurses, and/or data managers review lists of patients who have COVID-19 and will determine if there are patients who might be eligible for a clinical trial. The nurse/data manager reviews accessible medical records to screen further for eligibility. Subjects will be identified by their treating physicians. Clinical care team at Winship will inform potential subjects about the known benefits and potential risks of a clinical trial as well as other available treatment options. Some of the subjects recruited for this protocol will be patients being treated at Emory and under the care of one or more of the study investigators.

No incentives are provided to patients for trial participation.

Study personnel will notify Winship Central Subject Registration (WCSR) by email at [contact], once subject has been consented for a trial. Email notification must be done within 24 hours after consent has been obtained and it will include scanned copies of:

- Signed patient consent form
- HIPAA authorization form
- Emory Research Management System (ERMS; <https://erms.emory.edu>) Enrollment Fax Cover

The WCSR will enter the subject into the OnCore Research Management System, which is the system of record for Winship Cancer Institute Clinical Trials.

Participating Site (s)

Protocol Title: Duvelisib Ameliorates Manifestations of Pneumonia in Established Novel Coronavirus Infection (DAMPEN-CI)

A site- specific Central Subject Registration (CSR) form will be provided to Participating Site.

After each subject signs consent, the Central Subject Registration form is to be completed and sent to Winship within 24 hours of consent. This form, along with the valid, signed informed consent form/HIPAA authorization form, is to be faxed or emailed to Winship's Central Subject Registrar per instructions on the form. Once a subject is registered, each participating site will be notified via e-mail.

Enrolling a subject requires careful screening and determination of eligibility.

Eligible patients will be enrolled on study centrally at Winship Cancer Institute by the Study Coordinator.

When all required test results are available, complete the eligibility checklist and provide the checklist and the supporting documentation to the IRB approved investigator for review and sign-off. Once the investigator (sub-investigator, Co-Investigator) has signed the eligibility checklist, randomization and enrollment may proceed. Oncore and ERMS must be updated to reflect eligibility and on treatment status.

Following enrollment, patients should begin protocol treatment within 3 days. Issues that would cause treatment delays should be discussed with the Principal Investigator.

Screen failures:

After the screening evaluations have been completed, the investigator or designee is to review the inclusion/exclusion criteria and determine the participant's eligibility for the study.

Only the reason(s) for ineligibility will be collected on screen failures. Participants who are found to be ineligible will be told the reason(s) for ineligibility.

Individuals who do not meet the criteria for participation in this study (screen failure) because of an abnormal laboratory finding may be rescreened once

Participating site

The Eligibility checklist is to be printed from OnCore and verified by 2 people, of which one must be a clinical investigator or co-investigator. The completed and signed eligibility checklist along with all redacted supporting source documentation must be submitted to the Winship Multi-site Coordinator (MSC) or designee ([contact]) within 14 days after pre-registration but no later than 2 business days before the scheduled treatment visit. Eligibility will be confirmed by the site investigator or co-investigator and the MSC or designee within 1 business day of receipt of all eligibility documentation and confirmation will be sent to the participating site along with cohort assignment, if subject meets criteria. The Participating Site will enter all subject enrollment data in OnCore following eligibility confirmation, including subject 'on treatment date'. If a consented subject does not meet eligibility criteria (screen failure), the MSC will update the enrollment status in OnCore. The Participating Site is responsible for entering data for all procedures subject completed prior to eligibility determination.

Randomization between duvelisib 25 mg po BID and placebo BID will be stratified by study site. The investigational pharmacy will supply coded study drug based upon the results of central randomization.

12. Withdrawal of Participants

All study patients have the right to withdraw from the study at any time. The reasons for withdrawal must be documented in the case report form. Final study evaluations will be done at the time of withdrawal. The following are examples of early withdrawal from the study:

- Patient withdrawal of consent at any time

Protocol Title: Duvelisib Ameliorates Manifestations of Pneumonia in Established Novel Coronavirus Infection (DAMPEN-CI)

- Any medical condition that the primary investigator believes may jeopardize the patient's health or safety if they continue in the study
- Pregnancy
- Initiation of mechanical ventilation (e.g. intubation, high-flow O₂ Bi-PAP or AIRVO)
- Termination of the study by the Sponsor/Investigator, IDMC, the IRB, or the FDA

13. Risks to Participants

Safety of duvelisib:

Immune related toxicities are the most common non-hematological adverse event (AE) with duvelisib. Elevated AST/ALT and diarrhea are the most common non-hematological AEs. The rates of diarrhea ranged from 42-51% in clinical trials with a median onset of 2.2-4 months (28, 8). The median time of onset for AST/ALT elevation was 1.2 months and occurred in 39% of patients in one phase I clinical trial (28). Other non-hematological AE's that have been reported include:

- 1) risk of infection (reported in 61-69% of patients with upper respiratory tract infections and pneumonia being the most common infections (8, 29).) There have also been reports of *Pneumocystis jirovecii* with the use of duvelisib.
- 2) risk of pneumonitis,
- 3) risk of intestinal infection and colitis,
- 4) risk of severe skin reactions (maculopapular rash)
- 5) Neutropenia (the most common hematological AE, occurring in 29%-39% of patients in clinical trials)
- 6) pyrexia

Other Risks:

Risk of Phlebotomy- The primary risks of phlebotomy include local discomfort, occasional bleeding or bruising of the skin at the site of needle puncture, and rarely hematoma, infection, or fainting. At the time of enrollment and during study visits, each participant will be asked about participation in other research studies to ensure that blood draws do not exceed the following amounts for all research protocols combined: 10.5 mL/kg or 550 mL, whichever is smaller, over any 8-week period for adults, and no more than 5 mL/kg may in a single day (no more than 9.5 mL/kg may be drawn over any 8-week period) for persons under the age of 18.

Risk of Nasopharyngeal Swab- The primary risk of a nasal swab is local discomfort. Rarely, there can be local bleeding from the nasal mucosa, which is controlled with local measures such as pressure or packing with gauze.

Risk of Oropharyngeal Swab- The primary risk of an oropharyngeal swab is local discomfort. This swab can stimulate the gag reflex, and very rarely vomiting.

Risk of Endotracheal Aspirate- The primary risk of endotracheal aspirate is cough, and rarely can cause a small amount of bleeding.

Data security- Subjects will be asked to provide personal health information (PHI). All attempts will be made to keep this PHI confidential within the limits of the law. However, there is a chance that unauthorized persons will

Protocol Title: Duvelisib Ameliorates Manifestations of Pneumonia in Established Novel Coronavirus Infection (DAMPEN-CI)

see the subjects' PHI. All records will be kept in a locked file cabinet or maintained in a locked room at the participating sites. Electronic files will be password protected behind an academic institutional firewall. Only people who are involved in the conduct, oversight, monitoring, or auditing of this study will be allowed access to the PHI that is collected. Any publications from this study will not use information that will identify subjects. Organizations that may inspect and/or copy research records maintained at the participating sites for quality assurance and data analysis include groups such as the Food and Drug Administration (FDA).

14. Potential Benefits to Participants

There is no guarantee of benefit to subjects who enroll in this protocol.

15. Data Management and Confidentiality

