Objectives:	
Primary Objective:
 
1) To compare the incidence of the composite end-point of mechanical ventilation or death within 29 days of randomization in subjects with severe COVID-19 given placebo or oral duvelisib 
Secondary Objectives are to compare the duvelisib cohort to the placebo cohort with respect to:
 
2) Days to recovery as assessed by ACTT endpoints as the time to recovery (Day 1 through Day 29) to satisfy one of the following eight categories from the NIAID ordinal scale. The scale is as follows: 1) Death; 2) Hospitalized, on invasive mechanical ventilation or extracorporeal membrane oxygenation (ECMO); 3) Hospitalized, on non-invasive ventilation or high flow oxygen devices; 4) Hospitalized, requiring supplemental oxygen; 5) Hospitalized, not requiring supplemental oxygen - requiring ongoing medical care (COVID-19 related or otherwise); 6) Hospitalized, not requiring supplemental oxygen - no longer requires ongoing medical care; 7) Not hospitalized, limitation on activities and/or requiring home oxygen; 8) Not hospitalized, no limitations on activities.3) Duration of hospitalization4) Death within 29 days of randomization

Protocol Title: Duvelisib A meliorates Manifestations of Pneumonia in Established Novel Coronavirus Infection (DAMPEN-CI)

	
5) ICU transfer within 29 days of randomization6) Incidence of grade III-V adverse events or SAEs (as defined by NCI CTCAE version 5.0)7) Documented secondary bacterial or viral infection within 29 days of randomization.8) Mean frequencies of Th1 and Th17 T cells in blood mononuclear cells at 1, 2 and 4 weeks9) Mean levels of inflammatory serum biomarkers at 1, 2 and 4 weeks10) Gene expression profiles of T cells at 1, 2 and 4 weeks11) Median titers of IgG antibodies to SARS-CoV-2 at 4 weeks

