4.2.3. Product Storage and Stability

Duvelisib/placebo will be stored at the Emory Investigational Pharmacy. Duvelisib/study drugs will be stored at room temperature between 20-25 degrees Celsius.

4.2.4. Study Drug Administration:

Duvelisib/placebo is an oral medication that will be taken twice a day. The intent of the study design is to conduct a placebo-controlled double-blinded/double-masked administration of duvelisib or placebo in hospitalized

Protocol Title: Duvelisib Ameliorates Manifestations of Pneumonia in Established Novel Coronavirus Infection (DAMPEN-CI)

patients with severe COVID-19. All efforts will be undertaken to maintain ignorance among clinical and study staff as to allocation of each individual patient to active drug versus placebo—Subjects, the clinical team (physicians, nurses, advanced practice providers (nurse practitioner/physician assistant), clinical pharmacists) will not be informed as to whether an individual subject is receiving active drug or placebo.

4.2.5 Interruption/Disruption of Treatment:

Duvelisib/placebo is a BID medication. Medication doses that are missed or not absorbed (i.e., vomiting) will not be made up with additional dosing.

Duvelisib can be stopped if any of the following are observed:

- Grade 3 or 4 hematologic toxicity (19) as defined by the NCI CTCAE v5.0.
- Grade 3 or 4 non-hematological toxicity

Study drug (duvelisib or placebo) will be stopped at the time of hospital discharge if that occurs prior to day 15.

Grades 1-2 AEs as defined by the NCI CTCAE, version 5.0 will not result in any dose modifications and will be treated with supportive care. If study drug is stopped due to an AE, it will not be resumed.

5. Study Procedures

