Blood samples for chemistry, hematology, viral serologies, leukocyte immunophenotyping and pregnancy (for pre-menopausal patients) will be analyzed at Emory or secondary site clinical laboratories. The chemistry panel will include sodium, potassium, chloride, bicarbonate, glucose, BUN, AST, ALT, total bilirubin, total protein, ferritin, D-dimer, CRP will be tested at screening and on days 1, 8, 15, and 29. TSH will be tested at screening and at day 29. Hematology panel includes complete blood count, including white blood cell count with differential (neutrophils, lymphocytes, eosinophils, basophils), red blood cell count, hemoglobin, hematocrit and platelet count will be tested at screening and days 1, 8, 15, and 29. Hepatitis viral serologies will be tested at screening if a patient has a prior history of treated hepatitis B or C, and include:

- Hepatitis B Panel (HBsAg, HBsAb, HBcAb and HBV DNA PCR)
- Hepatitis C Panel (HCV Ab and HCV PCR)

Correlative Laboratory Data

- SARS-CoV-2 RT-PCR test from nasopharyngeal swabs will be ordered at screening [baseline, prior to study drug]. Results are returned as positive or negative, with Ct values for positive tests. Note: saliva SARS-CoV-2 PCR test will be added once available.
- Leukocyte immunophenotyping (via flow cytometry/fluorescence-activated cell sorting) will be done at days 1, 8, 15, and 29. This will determine the amount of B/T/NK cells and more specifically, the phenotypes and frequencies of these immune cell populations pre and post duvelisib exposure (Th1 and Th17 T cells).
- Mononuclear cells collected at days 1, 8, 15, and 29 will be stored for CyTOF analyses for more in-depth immune-phenotyping in follow-up studies.
- Blood cells collected at days 1, 8, 15, and 29 will also be collected in RNA stabilization tubes for immunological gene expression analyses.

Protocol Title: Duvelisib Ameliorates Manifestations of Pneumonia in Established Novel Coronavirus Infection (DAMPEN-CI)

- Mean levels of inflammatory serum biomarkers will be measured by ELISA at day 1 [baseline, prior to study drug], during and following 2 weeks of study drug exposure in each cohort, using samples at days 1, 8, 15, and 29
- Median titers of neutralizing antibodies to SARS-CoV-2 will be determined at days 1 and 29.

6. Data and Specimen Banking

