opportunity to stop the trial early due to futility or safety concerns. The only groups that will have access to unblinded interim data: (a) an independent data monitoring committee (IDMC); and (b) an independent statistical team whose role will be to generate the reports to be reviewed by the IDMC. The responsibility of any data-informed recommendations regarding continuing/stopping the study or modifying the study design/protocol be restricted to the IDMC.

Power Calculation

The reported incidence of death or mechanical intubation for patients with severe COVID-19 is approximately 40% (1). Local experience with COVID-19 patients at the Emory hospitals is consistent with this estimate, as 29% of all SARS-CoV-2 positive patients (n=800) are admitted to the ICU with COVID-19, and that 22% of all admitted patients are intubated, and 37% of intubated patients die in hospital. A favorable and clinically significant result from treatment with duvelisib in high-risk COVID-19 patients would be to reduce the composite incidence of death/mechanical ventilation from 40% to 15%. A sample size of 40 subjects for each treatment group will have >80% power to detect a 25% absolute reduction in the proportion of subjects who experience death or mechanical ventilation, comparing a predicted proportion of 40% death or intubation in the control arm to 15% death or intubation in the experimental arm receiving duvelisib treatment. The calculation is based on 10% type 1 error rate and two-sided Mantel-Haenszel test with one planned interim analysis when approximately 50% of sample enrolled (N=20/treatment). For

Analysis of Primary Endpoints

Analysis of the primary end-point will be based upon an intent-to-treat analysis of all subjects who are randomized to receive duvelisib/placebo. The primary endpoint is the proportion of patients who will require mechanical ventilation or experiencing death within 4-weeks (29 days) after randomization, which will be estimated with the corresponding 95% Clopper-Pearson confidence interval for the two arms separately. Fisher's Exact test will be used to test the difference between the two arms. In addition, a logistic regression will be used to estimate the odd ratio between the two arms controlling for the baseline covariates for an improved precision of the estimation (30).

Analysis of Secondary Endpoints

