At the time of study initiation at a non-Emory site, the Emory Sponsor-Investigator, Winship regulatory specialist, and Winship MSC will perform a site initiation teleconference. During this teleconference, the Emory team will review the study, enrollment, reporting, and regulatory compliance. Winship will have internal monitoring meetings. These meetings, which will include the participating site investigator, the clinical research coordinator and the regulatory affairs coordinator, will meet at least on a monthly basis to review and discuss study data to ensure subject safety. The research coordinators will maintain a spreadsheet which will be de-identified and will summarize all the patient data for subjects actively being treated on the trial as well as a roadmap detailing pending tests/treatments for each individual subject. The spreadsheet will be shared with the Emory PI via e-mail.

Winship's MSC will perform an on-site or remote monitoring visit within the first three months of enrollment of the first subject. Quarterly monitoring visits will occur (once annually onsite and three times remotely) until subject follow-up is terminated. Monthly reviews of data in OnCore will be conducted to ensure compliance or identify discrepancies; specifically, to assess compliance with the protocol, verify informed consent forms, verify compliance with SAE reporting procedures, monitor the tracking of study drug (pharmacy visit, storage and accounting of study drug), retrieve regulatory documentation, and perform quality control by comparing data from the CRF to the source documents of the center.

Study updates will occur at least once monthly between the PI at Emory and the research team at the participating site(s). The purpose of the meetings is to discuss the enrollment, regulatory updates, monitor toxicities, and evaluate the progress of the trial. Scheduled teleconferences may stop after all patients have completed assigned protocol therapy. The coordinating center (or designee) will communicate with participating sites via monthly email. The minutes from the teleconference will be maintained in the regulatory binder for the study. In addition, electronic copies will be sent via email to the principal investigators at each site.

17. Provisions to Protect the Privacy Interests of Participants

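### Section 11 has secondary sites sent each subject's cohort assignment with the eligibility confirmation, which, if followed literally, would tell them the arm and contradict the protocol's own blinding rule

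*Combined protocol and SAP*

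**What the plan says.** For subjects at participating (secondary) sites, Section 11 describes eligibility review by the site investigator and the Winship Multi-site Coordinator or designee. It then says that "confirmation will be sent to the participating site along with cohort assignment, if subject meets criteria".

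The next paragraph of Section 11 describes a blinded supply chain: "The investigational pharmacy will supply coded study drug based upon the results of central randomization". Section 1.2 (Schedule of Assessments) repeats this.

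Section 4.2.4 sets the blinding rule. "All efforts will be undertaken to maintain ignorance among clinical and study staff as to allocation of each individual patient", and subjects and the clinical team "will not be informed as to whether an individual subject is receiving active drug or placebo". Section 4.2.2 has all capsules over-encapsulated so that they look identical. Sections 5.1 and 15.1 call the trial double-blinded/double-masked.

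The protocol uses the word cohort for the treatment arms. The Synopsis states: "Secondary Objectives are to compare the duvelisib cohort to the placebo cohort with respect to". Section 5.6 refers to biomarkers measured "during and following 2 weeks of study drug exposure in each cohort".

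**The concern.** An operating instruction in Section 11 conflicts with the blinding rule. A coordinator who obeys it sends arm identity to a secondary site before the first dose. Identical capsules cannot undo that, and the information cannot be recalled once sent.

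Section 15.1 defines mechanical ventilation by examples that include high-flow oxygen, Bi-PAP and AIRVO, and the documents give no criterion for starting them. ICU transfer, hospital discharge (which also ends study drug under Section 4.2.5), stopping drug for an adverse event and judging its relatedness also rest with staff. Staff who know the arm could shift any of these, so the comparison could be biased at the sites concerned. Death, the other component of the composite, is less exposed.

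**Working it through.** **Step 1: what the sentence conveys.**

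| Question | What the documents show |
|---|---|
| What is sent? | Cohort assignment, with the eligibility confirmation (Section 11) |
| To whom? | The participating site, with no restriction to a pharmacist |
| What is a cohort? | The duvelisib or placebo arm (Synopsis, Section 2); same usage in Sections 5.6 and 16.1 |
| Is any other cohort defined? | No dose-level or disease cohort appears |
| Is the assignment said to be coded? | No |
| When? | On confirmation of eligibility, so before dosing |

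Read literally, the site learns the arm. Section 4.2.4 says that it must not. Both instructions cannot be followed.

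**Step 2: the plan's own figure.** No figure in the plan depends on this sentence. The stated power (over 80% for 40% versus 15%, 40 per arm, two-sided 10%) is not in dispute and reproduces. With pooled proportion 0.275:

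- SE under the null = √(2 × 0.275 × 0.725 / 40) = 0.0998
- SE under the alternative = √((0.40 × 0.60 + 0.15 × 0.85) / 40) = 0.0959
- power = Φ((0.25 − 1.645 × 0.0998) / 0.0959) = 81.5%

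**Step 3: illustration of what unblinding could do.**

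Inputs from Section 15.1: 40 per arm, 40% control event rate, two-sided 10% level, and Fisher's exact test for the primary endpoint.

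Assumptions not in the documents: no true drug effect; a share *f* of patients at unblinded sites; and a shift *d* in the recorded event rate there. The interim look is ignored.

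The overall rate in an affected arm becomes 0.40 ± *f* × *d*. For example, with *f* = 50% and *d* = 10 points, *f* × *d* = 0.05:

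- shift in the duvelisib arm only: 40% placebo versus 35% duvelisib
- opposite shifts in both arms: 45% versus 35%, a gap of 20 points between arms at the unblinded sites themselves

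The false-positive chance is the sum of Bin(a; 40, p_placebo) × Bin(b; 40, p_duvelisib) over all tables with a > b and Fisher p ≤ 0.10.

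| *f* | *d* (points) | Duvelisib arm only | Opposite shifts in both arms |
|---|---|---|---|
| no bias | 0 | 2.8% | 2.8% |
| 25% | 5 | 3.6% | 4.6% |
| 25% | 10 | 4.6% | 7.2% |
| 50% | 5 | 4.6% | 7.2% |
| 50% | 10 | 7.4% | 15.8% |

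The unbiased value is below 5% because Fisher's test is conservative at this sample size. Using the Mantel-Haenszel test without continuity correction, which Section 15.1 names for the power calculation, the corresponding chances are higher: 4.5% without bias, and 10.9% (one arm) or 21.7% (both arms) in the last row. Fisher's test is the relevant one because it is the stated primary analysis.

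**The case against.** The strongest reply is that this is stray wording and not a plan to unblind. Blinding is stated repeatedly: in 4.2.2, 4.2.4, 5.1, 15.1 and the coded-drug sentence directly after the paragraph at issue. The phrase may be left over from a template. Section 15.2 refers to ORR, CRS and neurotoxicity, and Section 16.2 to dose-limiting toxicities in phase I studies, neither of which belongs to this trial. That origin is plausible but is an inference. It does not change what a coordinator would do on following the sentence.

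Four stronger readings are tempting, and the documents do not support them.

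- *The blind is broken for every patient.* The sentence applies only to participating sites. These are described as potential (Section 10), although the study will seek to open at least one (Synopsis, Section 20). The lead-site process has no such sentence. The affected share could be zero.
- *The Multi-site Coordinator knows every arm and passes it by e-mail to the research team.* Section 11 does not name the sender or the means. The recipient is the site, which includes its own pharmacy staff.
- *The coordinator's monitoring is therefore compromised, so someone else must check drug accountability.* Sections 16.3 and 22 give the coordinator the monitoring visits. The reviews that "monitor the tracking of study drug (pharmacy visit, storage and accounting of study drug" are written in the passive. If the assignment is withheld and drug stays coded, accountability checks need not reveal the arm.
- *The primary result is bound to be biased.* The text supports only that it could be. In most rows of the one-arm illustration the false-positive chance stays below 5%.

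What stands of the objection is its limit on scope and certainty. The contradiction itself remains.

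**Conclusion.** Section 11, as worded for participating sites, contradicts Section 4.2.4 and its own coded-drug sentence, and must be corrected. This conclusion rests on the text alone: the literal content of the sentence, the consistent use of cohort for arm, and the absence of any statement that the assignment is coded or restricted.

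The size of any bias cannot be derived, because the documents give neither the secondary-site share nor the effect of knowing the arm. The illustrative range is 2.8% without bias, rising to about 7.4% to 15.8% with half of patients at unblinded sites and a 10-point shift. It shows only that the error could matter. The documents show a conflict of instructions that would unblind secondary sites if obeyed; they do not show that the sponsor intends to unblind or that any site has been unblinded.

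**What to change.** In Section 11, under Participating site, delete the words that add cohort assignment to the eligibility confirmation. State instead that the participating site's clinical and study staff and the Multi-site Coordinator receive only the confirmation and a coded subject or randomisation number, and that the arm-linked code goes only to the unblinded investigational pharmacy. Revise the matching registration form to agree.

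The cost is one protocol sentence and one form, with no extra patients, procedures or analyses. A separate person for drug accountability is not required.
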